4.1 Selection of Study Population

Approximately 50 patients will be screened of which, approximately 35 patients will be enrolled to target at least 26 patients as study completers at the appropriate number of study sites in the United States and Republic of Korea. At least 7 of the patients enrolled must be between 6 months through 12 months of age at the time of informed consent. Patients will be assigned to study treatment only if they meet all of the inclusion criteria and none of the exclusion criteria.

Deviations from the inclusion and exclusion criteria are not allowed because they can potentially jeopardize the scientific integrity of the study, regulatory acceptability, or patient safety. Therefore, adherence to the criteria as specified in the protocol is essential.

4.1.1 Inclusion Criteria

Each patient must meet all the following criteria to be enrolled in this study:

1. Parent(s)/caregiver(s) fully comprehend and sign the ICF in accordance with applicable laws, regulations, and local requirements, understand all study procedures, and can communicate satisfactorily with the investigator and study coordinator.
2. Is a male or female from 6 months through 36 months of age at the time of informed consent.
3. Has clinical diagnosis of IS, confirmed by video-EEG analysis, and hypsarrhythmia on EEG at screening according to the Burden of Amplitudes and Epileptiform Discharges (BASED) scale score.
4. As assessed by the investigator, has no or partial response to at least 2 out of the 3 therapies of ACTH, vigabatrin, and glucocorticoids (i.e. prednisolone), or has no or partial response to at least 1 out of the 3 therapies of ACTH, vigabatrin, and glucocorticoids and is contraindicated to and/or refused by the patient's legal representative(s) for treatment with 1 or both other 2 therapies.

5. Has general good health (defined as the absence of any clinically relevant abnormalities as determined by the investigator) based on physical and neurological examinations, medical history, normal renal function, and ECG, and clinical laboratory values completed during the Screening Period visit (Visit 1).
6. Parent(s)/caregiver(s) is willing and able to comply with the study procedures and visit schedules in the opinion of the investigator.

4.1.2 Exclusion Criteria

Patient meeting any of the following criteria will be excluded from the study:

1. Is considered by the investigator, for any reason (including, but not limited to, the risks described as precautions and warnings in the current version of the investigator's brochure for the investigational product) to be an unsuitable candidate to receive the investigational product.
2. Has known or suspected allergy to the investigational product.
3. Has known or suspected allergy to apple juice.
4. Has clinically significant renal impairment, defined as creatinine >1.5 mg/dL or blood urea nitrogen (BUN) $>2 \times$ upper limit of normal (ULN).
5. Has clinically significant liver dysfunction, defined as total bilirubin $\geq 2 \times$ ULN, or aspartate aminotransferase or alanine aminotransferase $\geq 3 \times$ ULN.
6. Has clinically significant abnormal laboratory values; the investigator may deem the patient eligible if he/she judges the laboratory values to be not clinically significant.
7. Has an ongoing or known history of human immunodeficiency virus infection, or chronic hepatitis B or C.
8. Has a clinically significant abnormality on ECG that, in the opinion of the investigator, increases the safety risks of participating in the study.
9. Has a neurodegenerative disorder as the underlying cause of IS.
10. Has a known history of aspiration pneumonia within the past year.
11. Has previously participated in another clinical study of the investigational product or received any investigational drug or device or investigational therapy within 30 days of study entry.

12. Has received therapy with felbamate, cannabinoids, ketogenic diet or vagus nerve stimulation within 14 days of screening.
13. Has received therapy with a medication known to be a CYP3A4 substrate and whose PK has been shown to be impacted in the presence of a CYP3A4 inhibitor within 14 days of screening (see [Appendix 13.3](#) for a non-exhaustive list of CYP3A4 substrates).
14. Has not remained at stable doses of all drugs used for treating epileptic seizures for at least 14 days prior to screening (except for rescue medications used for acute treatment of breakthrough seizures which are not known to be CYP3A4 substrates and whose PK has not been shown to be impacted in the presence of a CYP3A4 inhibitor [see [Appendix 13.3](#) for a non-exhaustive list of CYP3A4 substrates]).
15. Has a lethal or potentially lethal condition other than infantile spasms, with a significant risk of death before 18 months of age such as non-ketotic hyperglycinemia.
16. Has an underlying metabolic disease associated with glucose intolerance (e.g., glucose transporter deficiencies).
17. Has a body weight below 5 kg.

4.2 Withdrawal of Patients From the Study

4.2.1 Reasons for Withdrawal/Discontinuation

Patients may withdraw from the study at any time and for any reason without prejudice to their future medical care by the investigator or at the study site. Every effort should be made to keep patients in the study. The reasons for patients not completing the study will be recorded. Reasons for patients being withdrawn from the study may include:

- The patient does not meet the protocol inclusion or exclusion criteria.
- The patient's safety or welfare is at risk.
- The patient is noncompliant with the protocol, defined as failure to perform any portion of scheduled assessments or procedures.
- The patient has serious or intolerable AEs that, in the investigator's opinion, require withdrawal from the study.

- The patient is lost to follow-up.
- The patient's legal representative (parent(s)/caregiver(s)) withdraws consent or the investigator or sponsor decides to discontinue the patient's participation in the study.

The investigator will also withdraw a patient if Bio-Pharm Solutions Co., Ltd. terminates the study. Upon occurrence of a serious or intolerable AE, the investigator will confer with the sponsor. If a patient is discontinued because of an AE, the event will be followed until it is resolved. The patient's legal representative (parent[s]/caregiver[s]) may withdraw his or her consent at any time.

4.2.2 Handling of Withdrawals

Patients are free to withdraw from the study or study treatment at any time upon request. Patient participation in the study may be stopped at any time at the discretion of the investigator or at the request of the sponsor.

At the discretion of the investigator, patients who withdraw from the study prematurely may receive tapered doses of investigational product before discontinuing. The tapering schedule for early withdrawal patients will be determined on a case-by-case basis and the medical monitor will be available for assistance if needed. When a patient withdraws from the study treatment or active participation in the study, the reason(s) for withdrawal shall be recorded by the investigator on the relevant page of the electronic case report form (eCRF).

If a patient discontinues the study prematurely, investigator's assessment of efficacy and tolerability of the investigational product will be recorded on Visit 6 (\pm 5 days).

Whenever possible, all patients who discontinue study treatment or withdraw from the study prematurely will undergo all end-of-study (Visit 6) assessments. Patients who fail to undergo final assessments will be contacted by the study site in an attempt to have them comply with the protocol. Following a minimum of 2 documented unsuccessful telephone calls, a registered letter will be sent to the patient in a final attempt to ensure protocol compliance.

It is vital to obtain follow-up data on any patient withdrawn because of an AE or SAE. In every case, efforts must be made to undertake protocol-specified safety follow-up procedures.

4.2.3 Replacements

A total of approximately 50 patients will be screened of which around 35 patients will be enrolled to provide at least 26 completers. At least 7 of the patients enrolled must be between 6 months through 12 months of age at the time of informed consent. Patient screening and enrollment will be closed after 35 patients have begun Treatment Period 1. Patients who discontinue the study for any reason after dosing will not be replaced.

5 Study Treatments

5.1 Treatments Administered

[figure not shown]
[figure not shown]
Investigational product will be administered at 6 mg/kg, orally twice daily, once in the morning and 12 hours following the morning dose during the first 7 days of Treatment Period 1. Starting from the PM dose on the day of Visit 3, the dose will be escalated and patients will receive the investigational product at a dose of 9 mg/kg orally twice daily. Starting on Day 15, the dose will be escalated again and patients will receive the investigational product at a dose of 15 mg/kg orally twice daily until the end of Treatment Period 1. Each dose of the investigational product will be administered after at least a 2-hour fast. Food can be given 2 hours after dosing.

5.2 Identity of Investigational Product

The investigational product is a white to off-white powder. The dosage form received at each clinical study site is a glass bottle containing a nominal quantity of 100 mg of the powder JBPOS0101 active pharmaceutical ingredient (API) for reconstitution into an oral solution. Each JBPOS0101 API powder-in-glass bottle received at the clinical study site is individually enclosed in a heat-sealed aluminum foil pouch.

At the clinical study site, a pharmacist or authorized study personnel will dispense the JBPOS0101 API powder-in-glass bottle to the patient's caregiver without the heat-sealed aluminum foil pouch enclosure. Before dispensing, the pharmacist or authorized study personnel will adjust the content of the JBPOS0101 API powder-in-glass bottle to reflect the proper dose to be administered to the patient; the proper dose will be based on bodyweight and will be determined by the investigator. For the subsequent administration of the clinical material that will be performed by the patient's caregiver not at the clinical study site, the caregiver will be dispensed the customized doses of JBPOS0101 API powder-in-glass bottle in bulk packaging and will also be supplied with apple juice, an oral syringe and instructions for preparation of the solution for oral dosing. Other alternative dosing administration methods of the JBPOS0101 API powder-in-glass bottle may be permitted on a case-by-case basis with the approval of the sponsor and medical monitor.

The JBPOS0101 API powder-in-glass bottle is to be mixed with room temperature apple juice using the oral syringe supplied with the investigational product

[REDACTED]

Patients will be dosed the full amount of solution using the oral syringe. Patients may also be dosed the solution via gastrostomy or nasogastric tube. Each individual dose should be prepared and used immediately. Any unused apple juice remaining in the individual packages of apple juice after making the oral solution is to be discarded. Any used or unused JBPOS0101 API powder-in-glass bottle is to be returned to the study site for reconciliation.

5.3 Management of Clinical Supplies

5.3.1 Investigational Product Packaging and Storage

Investigational product API powder-in-glass bottles will be prepared in boxes, stored and shipped by Bio-Pharm Solutions' designee. There will be no randomization scheme and the medication will be dispensed at the study site by a pharmacist or authorized study personnel.

The JBPOS0101 API powder-in-glass bottle, and JBPOS0101 API powder-in-glass bottle enclosed in the heat-sealed aluminum foil pouch, should be tightly capped and stored at room temperature (15°C – 30°C), protected from moisture and direct sunlight. The apple juice provided by the study sites should be stored at room temperature. Adequate care should be taken when handling the dosage form to avoid breakage of the glassware.

The sponsor's designee will ship adequate supplies of the investigational product to the study sites.

5.3.2 Investigational Product Accountability

The investigator will maintain accurate records of receipt of all investigational product, including dates of receipt. In addition, the investigator must be able to account for all opened and unopened investigational product and accurate records will be kept regarding when and how many bottles of investigational product is dispensed and used by each patient, returned from each patient (if applicable), and disposed of at the site or returned to the sponsor or designee. Reasons for departure from the expected dispensing regimen must also be recorded. At the completion of the study, to satisfy regulatory requirements regarding drug accountability, all investigational product will be reconciled and retained or destroyed according to applicable regulations. All accountability records must be made available for

inspection by the sponsor and regulatory agency inspectors; copies must be provided to the sponsor at the conclusion of the study.

5.4 Overdose Management

An overdose is any dose of investigational product given to a patient that exceeds the dose described in the protocol. Any overdose, with or without associated AEs, must be promptly reported to the Sponsor Drug Safety Center. Overdoses without signs or symptoms do not need to be recorded as AEs; in case of any AEs associated with the overdose, these should be reported on relevant AE/SAE sections in the eCRF.

5.4.1 Treatment of Overdose

There is no known antidote for JBPOS0101. In case of suspected overdose, patients should be treated per standard medical practice based on the investigator's judgement. Dose delays and reductions may be implemented as necessary. Patients will be withdrawn from the study if persistent or unacceptable treatment-related toxicity is observed.

5.5 Blinding

This is an open-label study.

5.6 Treatment Compliance

Treatment compliance will be discussed with the patient's legal representative (parent[s]/caregiver[s]) by the study site staff at each visit, and noncompliance will be noted based on details the study site obtains at the patient visits. Any missed dose against the instructions will be recorded in the eCRF.

5.7 Prior and Concomitant Medication

Use of all concomitant medications will be recorded in the patient's eCRF. This will include all prescription drugs, herbal products, vitamins, minerals and over-the-counter (OTC) medications. The minimum requirement is that the medication name and the dates of administration are to be recorded. Any changes in concomitant medications will also be recorded in the patient's eCRF. Use of drugs known to be CYP3A4 substrates and whose PK has been shown to be impacted in the presence of a CYP3A4 inhibitor (see [Appendix 13.3](#) for a non-exhaustive list of CYP3A4 substrates) will not be allowed during the Screening

Period, Treatment Period 1, and Treatment Period 2; use of drugs known to be CYP3A4 substrates and whose PK has been shown to be impacted in the presence of a CYP3A4 inhibitor will not be allowed until 2 or more days after the investigational product has been discontinued. Except for drugs known to be CYP3A4 substrates and whose PK has been shown to be impacted in the presence of a CYP3A4 inhibitor, concomitant medications for treating non-epileptic seizure disorders are acceptable but changes in dose(s) are discouraged. Concomitant drugs used for treating epileptic seizures will be allowed during the study (excluding felbamate, cannabinoids, and drugs used for treating epileptic seizures known to be CYP3A4 substrates and whose PK has been shown to be impacted in the presence of a CYP3A4 inhibitor) if the doses remain stable during the Screening Period, Treatment Period 1, and Treatment Period 2 (with the exception that rescue medications used for acute treatment of breakthrough seizures which are not known to be CYP3A4 substrates and whose PK has not been shown to be impacted in the presence of a CYP3A4 inhibitor may be administered at any time during the study). Changes of dosages of drugs used for treating epileptic seizures are permitted 2 or more days after the investigational product has been discontinued. Ketogenic diet and vagus nerve stimulation therapies will not be allowed during the Screening Period, Treatment Period 1, and Treatment Period 2; ketogenic diet and vagus nerve stimulation therapies will not be allowed until 2 or more days after the investigational product has been discontinued.

All medications taken by patients after the Screening Period visit until the completion of the final Follow-Up visit will be documented as concomitant medications (medication, dose, treatment duration, and indication). The reported medications will be reviewed and evaluated by the investigator to determine if they will affect a patient's eligibility to participate or continue to participate in the study.

6 Study Assessments and Procedures

Before performing any study procedures, all legal representatives (parent[s]/caregiver[s]) of potential patients will sign an ICF. Patient's legal representative (parent[s]/caregiver[s]) will have the opportunity to have any questions answered before signing the ICF. The investigator must address all questions raised by the patient's legal representative (parent[s]/caregiver[s]). The investigator or designee will also sign the ICF.

Study visits and timing of assessments and procedures are presented in the schedule of events (SOE; [Appendix 13.1](#)).

6.1 Safety and Tolerability Assessments

Safety variables will include physical and neurological examination findings, vital sign measurements (blood pressure, pulse, and respiratory rate), height, weight, BMI, ECG tracings, clinical laboratory test results (hematology, serum chemistry, and urinalysis), and reporting of AEs.

Safety assessments will be conducted as shown in the SOE (Appendix 13.1).

6.1.1 Physical and Neurological Examination

A complete physical examination will be performed at the time points indicated in the SOE (Appendix 13.1). A complete physical examination will include assessment of skin, head, ears, eyes, nose, throat, neck, thyroid, lungs, heart, cardiovascular, abdomen, lymph nodes, and musculoskeletal system/extremities.

A neurological examination will be performed at the time points indicated in the SOE (Appendix 13.1). Where possible, a neurological examination will include mental status evaluation, examination of cranial nerves, motor examination (muscle tone, strength, and reflexes), cerebellar examination (coordination and gait), and sensory examination.

6.1.2 Vital Sign Measurements, Height, Weight, and Body Mass Index

Vital signs measurements will include blood pressure, temperature (measured rectally), pulse rate, and respiratory rate. Vital signs will be measured at the time points indicated in the SOE (Appendix 13.1).

Height, weight, and BMI will be measured at each clinic visit.

The investigator will determine whether any of the vital sign measurements are clinically significant or not clinically significant. Clinical significance is defined as any variation in results that has medical relevance and may result in an alteration in medical care (e.g., active observation, diagnostic measures, or therapeutic measures). If a clinically significant change from the screening values is noted, the clinically significant value and reason for clinical significance will be documented on the AE page of the patient's eCRF. The investigator will continue to monitor the patient with additional assessments until the value has reached the reference range, or the value at the Screening Period visit, or until the investigator determines that follow-up is no longer medically necessary.

6.1.3 Electrocardiograms

Single 12-lead ECGs will be obtained at the time points indicated in the SOE ([Appendix 13.1](#)). Electrocardiogram assessments will be interpreted locally and will include comments on whether the tracings are normal or abnormal; rhythm, presence of arrhythmia or conduction defects; morphology, any evidence of myocardial infarction, or ST segment, T Wave, and U Wave abnormalities. In addition, measurements of the following intervals will be measured and reported: RR interval, PR interval, QRS width, QT interval, and QTcF.

The investigator will determine whether any of the 12-lead ECG results are normal or abnormal, and if abnormal results are clinically significant or not clinically significant. Clinical significance is defined as any variation in results that has medical relevance and may result in an alteration in medical care (e.g., active observation, diagnostic measures, or therapeutic measures). If a clinically significant change from screening values is noted, the clinically significant value and reason for clinical significance will be documented on the AE page of the patient's eCRF and a pediatric cardiology consultation will be prompted. The investigator will continue to monitor the patient with additional assessments until either the value has reached the reference range, or the value at the Screening Period visit, or until the investigator determines that follow-up is no longer medically necessary.

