7.7.1 Analysis of Primary Safety Endpoint

Investigational Product Administration and Exposure: Investigational product administration and exposure will be summarized and listed. Further details on the investigational product administration and exposure calculation will be given in the SAP.

Medical History: Medical history details recorded at screening will be summarized and listed according to the coded MedDRA (latest version) by system organ class (SOC) and preferred term (PT).

Prior and Concomitant Medications: Prior and concomitant medications will be summarized according to the World Health Organization Drug Dictionary (WHODrug). The number and percentage of patients will be presented for previous and concomitant medications.

Adverse Events: AEs will be coded according to the coded MedDRA (latest version). Treatment-emergent AEs will be tabulated by SOC and PT. The following summary tables will be produced:

- TEAEs
- Treatment-related TEAEs
- TEAEs leading to investigational product discontinuation
- Treatment-related TEAEs leading to investigational product discontinuation

- Serious TEAEs
- Treatment-related serious TEAEs
- TEAEs leading to death
- Treatment-related TEAEs leading to death.

All AEs recorded during the study (including non-treatment-emergent AEs) will be listed.

Physical and Neurological Examination: Descriptive summaries of change in examination findings from baseline to post-baseline visits will be presented by test in a shift table (normal, abnormal [not clinically significant], and abnormal [clinically significant]).

Vital Signs: Descriptive by-visit summaries of vital signs data will be presented (including raw values and change from baseline). Vital signs will include blood pressures, temperature, pulse rate, and respiratory rate.

Height, Weight, and BMI: Baseline height, weight, and BMI will be summarized and listed.

ECGs: Descriptive summaries of change in overall assessment from baseline to post-baseline visits will be presented in a shift table (normal, abnormal [not clinically significant], and abnormal [clinically significant]). In addition, descriptive by-visit summaries of ECG data will be presented (including raw values and change from baseline). ECG data will include all of the following intervals: RR interval, PR interval, QRS width, QT interval, and QT interval from Fridericia's formula (QTcF).

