#### 7.12.4 Electrocardiograms

Continuous ECG parameters including RR interval, PR interval, QRS width, QT interval, and QTcF interval will be summarized by overall treatment and scheduled timepoints in terms of absolute values and change from baseline using descriptive statistics.

Shift tables will be presented that summarize the overall ECG interpretation as normal, abnormal not clinically significant, or abnormal clinically significant at baseline and each post-baseline time point.

ECG data will be listed by subject at each visit and time point collected with indicated clinically significant results.

ECG results meeting pre-specified criteria are listed and summarized. The following reference range ECG criteria by age range will be used.

Age Range	ECG Parameters	Lower Limit of Normal	Upper Limit of Normal
6-12 Months (including 12 th Month)	QT Interval	381 msec	449 msec
	QTcF Interval	350 msec	440 msec
>12-24 Months	QT Interval	381 msec	455 msec
	QTcF Interval	350 msec	440 msec
>24-36 Months	QT Interval	381 msec	455 msec
	QTcF Interval	350 msec	440 msec

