## **Section 16.2.8**

### **Individual Laboratory Measurements by Subject**

- Listing 16.2.8.1 Normal Ranges for Laboratory Data
- Listing 16.2.8.2 Clinical Laboratory Data by Category (Safety Population)
- Listing 16.2.8.3.1 Vital Signs (Safety Population)
- Listing 16.2.8.3.2 Weight, Height and BMI (Safety Population)
- Listing 16.2.8.4 Electrocardiogram Results (Safety Population)
- Listing 16.2.8.5 Electrocardiogram Results Meeting Prespecified Criteria (Safety Population)
- Listing 16.2.8.6 Physical and Neurological Examination Findings (Safety Population)
- Listing 16.2.8.7 COVID-19 Data (Safety Population)

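### The SAP's ECG criteria are absolute limits only: they miss within-range QTcF rises, do not separate new from pre-existing exceedances, and leave children with large rises uncounted

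*Protocol*

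**What the plan says.** **SAP 7.12.4 (Electrocardiograms).** Continuous ECG parameters, including QTcF, are summarised by "scheduled timepoints in terms of absolute values and change from baseline using descriptive statistics". A shift table compares the overall ECG interpretation at baseline with each later time point. The section then adds: "ECG results meeting pre-specified criteria are listed and summarized". The criteria are introduced with "The following reference range ECG criteria by age range will be used", and a table of lower and upper limits follows. For QTcF the limits are 350 and 440 msec in each age band. Nothing in the section refers these criteria to the child's baseline, restricts them to post-dose values, or grades results above the upper limit.

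**SAP section 8.** The only output named for these criteria is Listing 16.2.8.5. No summary table is listed for them.

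**SAP 7.1.** Descriptive statistics include the minimum and maximum. Listings give each subject's absolute and change-from-baseline values where applicable. Unscheduled and repeat assessments are listed but not summarised.

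**Protocol 6.1.3.** This section uses an absolute rating and a change rule. The first is the overall reading: "The investigator will determine whether any of the 12-lead ECG results are normal or abnormal, and if abnormal results are clinically significant or not". The second is "If a clinically significant change from screening values is noted, the clinically significant value and reason for clinical significance will be documented" as an adverse event.

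**Protocol 7.7.1.** The planned ECG analysis is a shift table of overall assessment, plus by-visit raw values and change from baseline. It sets no outlier categories.

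**Protocol 4.1.2, exclusion 8.** A child is excluded if the child "Has a clinically significant abnormality on ECG that, in the opinion of the investigator, increases the safety risks of participating in the study". There is no numeric QTcF limit for entry.

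**The concern.** ECG findings are among the primary safety endpoints (Protocol 7.1, SAP 2.4.1). The trial is open-label with no control arm, so each child's own baseline is the only comparator. A criterion that ignores baseline can pass over a child whose QTcF rose a long way within the range. It can also pick out a child whose QTcF was outside the range before the first dose and did not move.

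The SAP treats laboratory data differently. Section 7.12.2 plans a shift from baseline by normal range (Table 14.3.4.3). QTcF has a stated normal range but no equivalent shift.

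At stake is whether the study report can say how many children had a large QTcF increase, and how many crossed the limit only after dosing. As planned, a reader would have to work out both by hand from the listings.

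**Working it through.** The documents give no expected number of ECG outliers, so there is no planned figure to reproduce. The check covers the QTcF row only.

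**Inputs**
- QTcF limits 350 and 440 msec, all ages (SAP 7.12.4).
- ECGs at screening and Days 7, 28 and 42 (SAP 3.8.4). Baseline is the last value before first dose (SAP 7.1), so it is normally the screening ECG.
- Single ECGs at each time point (Protocol 6.1.3).
- 35 children dosed (Protocol 4.2.3).

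**Step 1: size of the unflagged rise, from the SAP's limits alone.** For a baseline b within limits, the largest rise that stays in range is 440 − b.

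| Baseline QTcF (msec) | Largest unflagged rise (msec) |
|---|---|
| 350 | 90 |
| 380 | 60 |
| 400 | 40 |
| 420 | 20 |
| 440 | 0 |

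Conversely, a rise of d is unflagged when 350 ≤ b ≤ 440 − d. A 30 msec rise is missed from baselines of 350 to 410, and a 60 msec rise from 350 to 380.

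**Step 2: three cases under the rule as written**
- 360 to 435 (+75): not flagged.
- 440 to 441 (+1): flagged.
- 445 to 442 (−3): outside the limit before and after, and nothing in the rule sets it apart from a new exceedance.

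**Step 3: where the +75 msec child would appear**
- Table 14.3.5.2 (observed values and change): in the mean, and as the maximum if it is the largest rise at that visit. There is no count of such children.
- ECG listing 16.2.8.4, read with SAP 7.1: identifiable individually, with the change value where applicable.
- Table 14.3.5.3 (shift): only if the local overall interpretation changes.
- Adverse event records: only if the investigator judges the change clinically significant.
- Listing 16.2.8.5: not on the QTcF criterion.

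**Step 4: illustration under assumed baselines.** The documents give no QTcF distribution. Assume normal baselines with mean m and SD s. Among children starting within limits, the share whose rise d is missed is

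[Φ((440 − d − m)/s) − Φ((350 − m)/s)] / [Φ((440 − m)/s) − Φ((350 − m)/s)].

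For m = 395, s = 20:
- d = 30: (0.773 − 0.012)/(0.988 − 0.012) = 0.78.
- d = 60: (0.227 − 0.012)/(0.988 − 0.012) = 0.22.

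Over m = 385 to 405 and s = 15 to 25, the share missed is about 62% to 95% for a 30 msec rise and 5% to 38% for a 60 msec rise. The expected number starting above 440 is 35 × P(b > 440), about 0 to 2.8 children. These ranges follow from the assumed means and SDs and are not expected rates for this trial.

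**The case against.** **No conflict with the protocol.** A reader might infer that the protocol judges ECG safety by change from screening and that the SAP departs from it. The documents do not support that. Protocol 6.1.3 also requires an absolute rating, and follow-up may end at either the reference range or the screening value. Its change rule governs what the investigator records. The planned analysis is in Protocol 7.7.1, and SAP 7.12.4 delivers all of it before adding the reference limits. This objection stands in full.

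**Large rises are not lost.** Step 3 shows several places where they can be seen. With about 35 children and three scheduled post-dose ECGs each, individual review is practical. This also stands; what is absent is a categorical count. The maximum in Table 14.3.5.2 shows one extreme per visit, not how many children had a large rise or whether the same child recurs.

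**The flag does respond to the drug.** A reader might infer that it mainly reflects where a child started. Illustrative figures point the other way. With assumed baseline mean 400 and SD 20, 2.3% exceed 440 before dosing and 30.9% after a uniform 30 msec rise, so (30.9 − 2.3)/30.9 = 93% of the flags come from the rise. With mean 410 and SD 25, the figures are 11.5% and 50%, and the share is (50 − 11.5)/50 = 77%. A uniform rise would also show directly in the mean-change table.

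**Eligibility.** Besides exclusion 8, inclusion criterion 5 (Protocol 4.1.1) requires general good health based partly on the ECG. That makes entry above 440 less likely but does not rule it out, since both criteria rest on investigator judgement. Nor would such a child necessarily meet the criterion at every visit, because single ECGs vary.

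**Counting.** That children above 440 at entry would be counted as outliers is an inference. With no summary table in section 8, the count is undefined.

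**Conclusion.** The point holds as a gap in SAP 7.12.4. The pre-specified criteria are absolute limits only. By arithmetic on those limits, they leave unflagged a QTcF rise of up to 90 msec that stays in range. They do not separate values newly outside the limit after dosing from values already outside it at baseline. No planned output counts children with a large rise, and the promised summary of results meeting the criteria has no table in section 8.

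These conclusions need no distributional assumption; the percentages do, and serve only as illustration. The documents do not support reading this as a contradiction of the protocol or as a loss of large rises from the analysis. It is a worthwhile, inexpensive improvement to how a primary safety endpoint is summarised.

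**What to change.** Amend SAP 7.12.4 and section 8 before database lock:

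1. Count a result as meeting the criteria only if it is outside the limit after dosing and was not outside it at baseline. Show cases already outside the limit at baseline separately.
2. Add n/N for each child's maximum QTcF increase from baseline in fixed categories, and graded bands above the upper limit. The sponsor should choose and justify the cut-offs for this age group. State whether unscheduled ECGs contribute to the maximum, since SAP 7.1 otherwise leaves them out of safety summaries.
3. Add the matching summary table to section 8, alongside Listing 16.2.8.5.

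The cost is SAP wording and one table. It uses ECGs already collected and changes no clinical procedure. The downside is that, with single ECGs, some small rises will be measurement noise, so the lowest category should be read with that in mind.
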